## 1) Protocol Title

Comparison of 2 application techniques for LET (lidocaine 4%; epinephrine 0.1%; tetracaine 0.5%) gel used prior to simple laceration repair

## 2) HSC Review History

n/a

## 4) Objectives\*

Describe the purpose, specific aims, or objectives.

State the hypotheses to be tested.

**Primary outcome:** To compare pain scores during laceration repair with first suture placement using standardized visual analog scale (VAS) between 2 different topical local anesthetic application techniques for using LET gel. Specifically, we are looking to see if applying LET gel 3 times, spaced 10 minutes apart (triple LET) provides superior anesthesia to one 30 minute application (single LET). Single LET is the current standard method of application.

### Secondary outcomes:

- 1) To compare provider satisfaction scores using a Likert scale between the triple LET and single LET application techniques.
- 2) To compare parental satisfaction scores using a Likert scale between the triple LET and single LET application techniques.
- 3) To compare the need for additional local anesthetic infiltration between the triple LET and single LET application techniques.

**Hypothesis:** We believe that applying LET gel 3 times over a 30 minute period will provide superior anesthesia to one 30 minute long application.

## 4) Background\*

Describe the relevant prior experience and gaps in current knowledge.

Describe any relevant preliminary data.

Provide the scientific or scholarly background for, rationale for, and significance of the Human Research based on the existing literature and how will it add to existing knowledge.

Preventing pain in the pediatric emergency department is a high priority. Studies have shown that sub-therapeutic anesthesia may result in more procedural complications, increased sensitivity to pain in the future, and increased anxiety related to medical care.

LET gel has been shown to be safe and effective when used prior to wound repair.

At our institution, the current method used to apply the LET gel is one 30 minute application. This is the standard application method. However, other institutions anecdotally report using different application techniques with superior results, specifically, applying the LET gel 3 times, in 10 minute intervals over a 30 minute period.

There are no studies comparing these 2 application techniques. We have only anecdotal reports that the triple LET application technique decreases patient pain and reduces the need for additional anesthetic infiltration.

## 5) Setting of the Human Research

Describe the sites at which your research team will conduct the research. If applicable, describe:

We are a county hospital with a Pediatric ED, level 1 trauma center that sees ~24000 patients aged < 21 years annually. We have Pediatric Emergency Medicine (PEM) trained physicians, PEM fellows, pediatric and emergency medicine residents, family medicine residents, medical students, and pediatric nurse practitioners working in our pediatric emergency department.

Identify the site(s) where your research team will identify and recruit potential subjects.

We will identify and recruit potential subjects from those presenting to the Pediatric Emergency Department.

Identify the site(s) where your research procedures will be performed.

The research will be conducted within the Harbor-UCLA Medical Center Pediatric Emergency Department.

Composition and involvement of any community advisory board.

N/A

## 7) Resources Available to Conduct the Human Research

Justify the feasibility of recruiting the required number of suitable subjects within the agreed recruitment period. For example, how many potential subjects do you have access to? What percentage of those potential subjects do you need to recruit?

We are a county hospital with a Pediatric ED, level 1 trauma center that sees ~24000 patients aged < 21 years annually. Of these there are a number who will present with a laceration requiring repair.

We will be studying a convenience sample of patients requiring simple laceration repairs; enrollment will be centered around availability of investigators.

Sample size calculations revealed that enrolling 22 patients per group would have 90% power to detect a 1 point difference in visual analog pain score (range 0-10) between groups with a standard deviation of 1, using a two sample t test with an alpha of 0.05. We estimate that the enrollment will be complete within 1 year after IRB approval.

Describe the time that you will devote to conducting and completing the trial within the agreed trial period.

The Principal Investigator will devote ~5 hours a week/month to conducting this study. The fellows involved will devote ~20 hours a week/month.

Describe the number and qualifications of your staff, their experience in conducting research, their knowledge of the local study sites, culture, and society.

We will have 2 fellows enrolling patients in the Pediatric ED.

Drs. [name], [name], and [name] developed the study design and will be involved in data collection, analysis, and manuscript preparation.

All members of the research team have completed CITI training. The team includes:

**[name] MD, MS, FACEP, FAAP:** [name] is a pediatric emergency medicine fellowship trained Clinical Professor of Pediatrics, the pediatric emergency medicine fellowship director, and has a Master of Science in Epidemiology and experience in research regarding pain with procedures. She is a reviewer for eight journals, an associate editor for Annals of Emergency Medicine, has been principal investigator or co-investigator on several projects including as recipient of a K23 award. She has coauthored 13 peer-reviewed manuscripts.

**[name]:** [name] is a pediatric emergency medicine fellow with prior research experience. He completed his residency in pediatrics. He anticipates completing his fellowship in June 2017.

**[name]:** [name] is an ultrasound fellow in the emergency department. He completed his residency in emergency medicine. He has prior research experience and is involved in several studies in the emergency department.

*Describe your facilities.*

Facilities: Harbor-UCLA Medical Center has an 18 bed pediatric emergency department that sees about 24,000 patients per year.

*Describe the availability of medical or psychological resources that subjects might need as a result of an anticipated consequences of the human research.*

We do not anticipate the need for any additional medical or psychological resources for the subjects as a result of our research. The patients will be consented for two known techniques of LET gel application, both of which are considered appropriate for pre-laceration repair analgesia. Treatment will not be withheld from the subjects.

*Describe your process to ensure that all persons assisting with the trial are adequately informed about the protocol, the investigational product(s), and their trial-related duties and functions.*

The investigators will meet regularly to discuss the status of the study and their roles and duties.

## 8) Prior Approvals

*Describe any approvals that will be obtained prior to commencing the research. (E.g., school, external site, funding agency, laboratory, radiation safety, or biosafety approval.)*

CITI training and IRB approval as required by LA BioMed. No additional product approvals will be required.

## 9) Study Design

### a) Recruitment Methods

*Describe when, where, and how potential subjects will be recruited.*

Subjects will be identified on a convenience sample basis when a study investigator is available. When a study investigator is available, the patient will be identified on ORCHID, the patient/family will be approached by the treating clinicians and asked for permission for the researcher to approach and discuss the study.

*Describe the source of subjects.*

The source of potential subjects will be those presenting to the Pediatrics ED with a laceration requiring repair and meeting the study inclusion criteria.

*Describe the methods that will be used to identify potential subjects.*

## LET Comparison Study

Revised: June 22, 2016

Subjects will be identified on a convenience sample basis when a study investigators are available. When a study investigator is available, the patient will be identified on ORCHID, the patient/family will be approached by the treating clinicians and asked for permission for the researcher to approach and discuss the study.

### Describe the amount and timing of any payments to subjects.

Subjects will not be compensated for their participation in this study.

### Describe materials that will be used to recruit subjects. Include copies of these documents with the application. For advertisements, submit the final copy of printed advertisements. When advertisements are taped for broadcast, provide the final audio/video tape. You may submit the wording of the advertisement prior to taping to preclude re-taping because of inappropriate wording, provided the HSC reviews the final audio/video tape.

There will be no advertisements.

## **b) Inclusion and Exclusion Criteria\***

### Describe how you will screen for eligibility.

When a study investigator is available, the patient will be identified on ORCHID, the patient/family will be approached by the treating clinicians and asked for permission for the researcher to approach and discuss the study.

### Describe the criteria that define who will be included or excluded in your final study sample.

#### Inclusion Criteria:

- Patients with simple ( $\leq 3$  cm) lacerations who are  $\geq 7$  years old and  $\leq 18$  years old, for whom the physician plans to close the laceration using simple superficial interrupted sutures.

#### Exclusion Criteria:

- Lacerations involving the hands, feet, genitals, tongue, mucus membranes, nose, ears, or occurring over joints.
- Patients who are developmentally delayed or have a disability preventing them from giving a reliable pain score.
- Patients whose primary language is other than English or Spanish.
- Patients for whom procedural sedation is required.
- Patients receiving intranasal or oral midazolam or inhaled nitrous oxide.

## **c) Local Number of Subjects**

### Indicate the total number of subjects to be accrued locally.

If applicable, distinguish between the number of subjects who are expected to be enrolled and screen, and the number of subjects needed to complete the research procedures (i.e., numbers of subjects excluding screen failures.)

We will be recruiting subjects on a convenience sample basis. We have calculated the need to recruit 22 subjects in each arm, for a total of 44 subjects, to have a 90% power to detect a 1 point difference in pain score, with an alpha of 0.05.

## **d) Study-Wide Number of Subjects\***

### If this is a multicenter study, indicate the total number of subjects to be accrued across all sites.

N/A

## **e) Study Timelines\***

### Describe:

- The duration of an individual subject's participation in the study.

- The duration anticipated to enroll all study subjects.
- The estimated date for the investigators to complete this study (complete primary analyses)

The enrolled patients will be involved in the study through the duration of the consent process, laceration repair, and time needed to obtain pain score after procedure. There will be no follow-up beyond the ED visit.

Estimated date to complete enrollment is 1 year after IRB approval.

Estimated date to complete data analysis and manuscript is 2 years after IRB approval.

### **f) Study Endpoints\***

Describe the primary and secondary study endpoints.

Describe any primary or secondary safety endpoints.

**Primary endpoint:** To compare pain scores during laceration repair with first suture placement using standardized visual analog scale (VAS) between 2 different topical local anesthetic application techniques for using LET gel. Specifically, we are looking to see if applying LET gel 3 times, spaced 10 minutes apart (triple LET) provides superior anesthesia to one 30 minute application (single LET).

**Secondary endpoints:**

- 1) To compare provider satisfaction scores using a Likert scale between the triple LET and single LET application techniques.
- 2) To compare parental satisfaction scores using a Likert scale between the triple LET and single LET application techniques.
- 3) To compare the need for additional local anesthetic infiltration between the triple LET and single LET application techniques.

### **g) Procedures Involved in the Human Research\***

Describe and explain the study design.

Provide a description of all procedures being performed and when they are performed, including procedures being performed to monitor subjects for safety or minimize risks. Include procedures being performed already for diagnostic or treatment purposes and differentiate between these and the procedures performed solely for the research.

Once patients are identified and consent is obtained, they will be randomized to one of two groups. One group will have LET gel applied to the laceration one time for a duration of 30 minutes. The other group will have LET gel applied 3 times, at 10 minute intervals. Between applications, the excess gel on the surface of the skin will be gently wiped off, and a new strip of LET gel will be applied. The laceration repair will proceed in a normal sterile fashion, using standard irrigation and debridement techniques. Laceration repair will occur within the 15 minutes following the 30 minute period of LET application to the wound. The patient will be asked to rate his/her pain immediately after the first suture is placed or attempted using the visual analogue scale (VAS, range 0-10). The decision to use any additional anesthetic infiltration will be left to the performing provider. There will be 2 nurses involved in the study. One nurse will be the patient's primary nurse and will be administering the LET gel (so will not be blinded, but will not be involved in data collection). The other nurse will be obtaining the VAS immediately (Appendix 3) after the first suture is placed, using a pre-prepared script (Appendix 3) and standardized technique. The nurse or research assistant will also be blinded as to the method of LET gel application. The provider performing the laceration repair will be blinded. The research assistant will not be blinded and will coordinate all involved providers and nurses, will ensure correct timing in LET gel administration, and laceration repair timing.

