## LET Comparison Study

Revised: June 22, 2016

The investigator will interview for demographic data, ensure proper application of LET gel according to randomized group, observe laceration repair, record use of additional anesthesia, (including all data collection on data form).

Describe procedures taken to lessen the probability or magnitude of risks.

Risks to the patient are minimal given that LET is routinely used in the pediatric ED and has been shown to be efficacious. To minimize risk, patients and/or clinicians can withdraw from the study at any time.

Identify which procedures are being done as part of the Human Research and which are being conducted anyway for other reasons.

The randomization to the timing and number of applications of LET gel is being done specifically for this study as are the VAS post placement of first suture. Repair of the laceration will be done as part of standard of care.

Describe all drugs and devices used in the research and the purpose of their use, and their regulatory approval status.

LET gel is compounded by our pharmacy using the formula shown in Appendix 2.

Describe the source records that will be used to collect data about subjects. Attach all surveys, scripts, and data collection forms.

The attached survey forms can be seen in Appendices.

Describe what data will be collected including long-term follow-up.

There will not be any long-term follow up.

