## 12) Provisions to Protect the Privacy Interests of Subjects

Describe the steps that will be taken to protect subjects' privacy interests. "Privacy interest" refers to a person's desire to place limits on whom they interact or whom they provide personal information.

Describe what steps you will take to make the subjects feel at ease with the research situation in terms of the questions being asked and the procedures being performed. "At ease" does not refer to physical discomfort, but the sense of intrusiveness a subject might experience in response to questions, examinations, and procedures.

Indicate how the research team is permitted to access any sources of information about the subjects.

A provider will approach and ask patient and parent or legal guardian for permission for a researcher to approach patient/family. The investigator will discuss the study design with the family and assure that medical care will not be withheld as part of this study. The investigator will inform the patient and family that they can withdraw from the study at any time. The investigator will explain to the patient and family that the information recorded on the data collection forms will not include any direct identifiers and will only be accessible to the study investigators. The patient and family will be assured that their involvement in this study is completely voluntary, and their decision to take part in the study will not affect the care they receive.

All interactions with the subjects and their parent/legal guardian will take place in a private setting such as a private exam room.

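### Does the plan need changing because the child who scores pain and the parent who scores satisfaction can tell which LET technique was used?

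*Combined protocol and SAP*

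**What the plan says.** Section 9 g) of the combined protocol and SAP assigns blinding role by role. The nurse who obtains the VAS is blinded. For the operator it states: "The provider performing the laceration repair will be blinded". The primary nurse, who applies the gel, is not blinded and collects no data. The child and the parent appear in none of these statements, nor in any other part of the text supplied.

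The child gives the primary score, straight after the first suture. The parent supplies the second secondary endpoint in section 9 f): "To compare parental satisfaction scores using a Likert scale between the triple LET and single LET application techniques".

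The single arm has one undisturbed 30-minute application. In the triple arm, before each new application, "the excess gel on the surface of the skin will be gently wiped off, and a new strip of LET gel will be applied". No corresponding contact is described for the single arm.

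Families know both options. Section 7 says: "The patients will be consented for two known techniques of LET gel application, both of which are considered appropriate". Section 12 adds: "The investigator will discuss the study design with the family". Section 17 has guardians repeat the plan back.

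Section 9 f) frames the primary comparison as one "between 2 different topical local anesthetic application techniques for using LET gel". Infiltration is a secondary endpoint, and section 9 g) says: "The decision to use any additional anesthetic infiltration will be left to the performing provider".

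**The concern.** The primary endpoint is a self-report, and the person reporting can see or feel which arm they are in. A blinded nurse with a script limits the assessor's influence but does not mask the child. A parent in the room could also see the re-application; the text does not say whether parents are present for it. The triple arm receives two further nurse contacts, inferred to fall at about 10 and 20 minutes.

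Part of a VAS or parental-satisfaction difference could therefore come from expectation or attention and not from deeper anaesthesia. The protocol's hypothesis is that triple application gives better anaesthesia, and no text limits how a difference will be read. A larger sample would not remove such a shift. It is natural to ask for matched contacts, partial masking and a pre-written restriction on the conclusion.

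**Working it through.** **Inputs from the plan** (sections 7 and 9 c)): 22 per arm, difference 1 point on a 0–10 VAS, SD 1, two-sample t test, alpha 0.05. Sidedness is not stated, but the two-sided calculation reproduces the stated number.

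**The plan's own figure.** The standard error is SD × √(2/22) = 1 × 0.3015. The noncentrality is 1/0.3015 = 3.317 on 42 df, and the two-sided power is 89.97%. The stated 90% reproduces, and the blinding question does not alter it. The smallest significant observed difference is 2.018 × 0.3015 = 0.61 points.

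**Effect of an assumed reporting shift.** The documents give no figure for a shift. The values below are illustrations, as are SDs of 2 and 3. With no true difference, noncentrality = shift/(SD × 0.3015), 42 df. The entries are the probability of p<0.05; the nominal value is 5%.

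| SD | shift 0.25 | shift 0.5 |
|---|---|---|
| 1 (plan) | 12.8% | 36.7% |
| 2 | 6.9% | 12.8% |
| 3 | 5.8% | 8.4% |

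The largest entry needs the larger shift together with the smallest SD. Nothing in the documents shows that a shift would favour triple LET. Section 7 treats both techniques as appropriate, no supplied text says families are told which is expected to do better, and repeated wiping could raise distress.

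**What the blinded provider's outcome can add.** Fisher exact test, 22 per arm, both binomials fully enumerated, assumed infiltration rates: power is 27.7% for 30% vs 10%, 54.6% for 40% vs 10%, and 78.6% for 50% vs 10%. An illustrative 7/22 vs 2/22 is a difference of 31.8% − 9.1% = 22.7 points, Newcombe 95% CI −1.6 to 44.6. Infiltration can support the VAS result but cannot replace it.

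It is also only partly protected. Under section 9 g), the investigator who checks that the gel is applied as randomised also observes the repair and records extra anaesthesia. Nothing in the text stops a family from telling the provider the arm.

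**What each possible change would achieve.**

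1. *Matched visits at 10 and 20 minutes with the wound screened.* This costs 2 × 22 = 44 extra contacts, plus screening in all 44 children. The child still feels wiping in one arm only, so the primary rater stays unmasked. A child of at least 7 can tell the parent, so masking of the parent is fragile too. Section 4 defines the comparator as the current standard method, and scheduled visits and screening depart from it. Parental satisfaction is a rating of the technique, and screening would hide part of what is rated.
2. *A pre-written restriction on the conclusion, read alongside infiltration and provider satisfaction.* This changes neither data nor analysis. It would also present the provider outcomes as better protected than the text supports.
3. *Collecting allocation guesses descriptively.* This has no bearing on the conclusion.

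**The case for a change.** The strongest reply is that unblinded self-report on a primary endpoint is a real threat, the hypothesis is worded as better anaesthesia and not as a better technique overall, and two sentences of text cost almost nothing. A researcher is present throughout in both arms (section 15), so general attention is partly balanced, but the re-application contacts are not. The wound need not be touched in the single arm, and the visits could be described truthfully at consent.

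Much of this stands. Both ratings should be treated as unblinded, and the contacts do differ. What does not stand is the step to a changed design. The nurse contacts cannot be separated from re-application. If discomfort from wiping counts as part of the technique, the visit needed to wipe counts as well. A technique-against-technique comparison is legitimate, and section 9 f) sets one up. Describing unblinded self-report as a limitation is ordinary reporting, and a competent author would do it without an instruction in the protocol.

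Two cautions remain. Section 9 g) says "The attached survey forms can be seen in Appendices", but those forms, the VAS script and the consent documents are not in the text supplied, so the finding is that blinding of child and parent is not stated here, not that it is absent everywhere. Section 9 g) also calls the research assistant both blinded and not blinded. That is a separate inconsistency and does not affect what the child or parent can perceive.

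**Conclusion.** The facts are right: in the supplied text neither the child nor the parent is blinded, and only one arm is wiped and re-treated. No change to the plan follows, because this is a fair trade-off in comparing two visibly different techniques. The available remedy does not mask the primary rater, and it alters both the standard-practice comparator and what parents are asked to judge.

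The possible distortion ranges from negligible to substantial: 5.8% to 36.7% false-positive probability for assumed shifts of 0.25 to 0.5 points and SDs of 1 to 3. Every shift is an assumption, and the direction is unknown. A VAS difference should be read as a difference between techniques as delivered, with the child's score and the parent's rating described as unblinded and the provider's outcomes as only partly protected. Analysts can do this when reporting, under the plan as written.
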